### 10.2 Analysis Populations

The following populations will be considered for analysis of various endpoints:

- *Intent-to-Treat Population (ITT)*: Includes all randomized subjects according to the randomized treatment assignment.
- *Per-Protocol Population (PP)*: Include all subjects in the ITT population without major protocol deviations which may affect the evaluation of the primary efficacy endpoints. For analysis purposes, subjects will be grouped according to the actual treatment received.
- *Safety Analysis Population*: Consists of all randomized subjects that received at least one dose of the assigned treatment according to the treatment received.

Per protocol population is based on the actual deviations, the criteria for exclusion of subjects from the different data sets will be specified and updated, if necessary, prior to database lock.

### **10.3 Planned Analyses**

All efficacy and safety endpoint parameters will be summarized descriptively. Continuous efficacy and safety endpoints will be summarized using the mean, standard deviation, median, minimum and maximum, 25 and 75 percentiles). Frequency distributions (counts and percentages) will be used to summarize categorical endpoints.

Once all patients complete the study evaluation (i.e., nominal study Week 24 or 26) or prematurely discontinued and the final database is locked, the study will be unblinded and final analyses will be performed. Analysis will be based on nominal study visits (i.e., study Weeks 0 to 26).

The primary efficacy hypothesis tests will be performed using a 2-sided 0.05 significance level. For secondary endpoints, adjustments for the overall type I error will be performed.

It is anticipated that statistical summaries will be performed using SAS Version 9.4 (SAS Institute, Inc., Cary, NC, USA) or higher. Additional software may be used to produce graphics and for statistical methodology not available in SAS.

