### 7.4 Unscheduled Visits

Subject visits conducted outside of the scheduled protocol visits should be captured in the subject's medical record and CRF.

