### **10.3.9.3 Change from Baseline in Laboratory Values**

For selected hematology and chemistry laboratory tests performed, change from Baseline will be calculated for each subject and study visit. Box plots indicating mean and median as well as the 25th and 75th percentiles, and/or spaghetti plots will be presented by treatment group and study visit for both raw values and changes from Baseline.

Summary statistics (i.e., mean, median, standard deviation, maximum, and minimum, 25th and 75th percentiles) for the actual values, changes from Baseline, and maximum value observed post treatment will be tabulated by treatment group and study week. In addition, shifts based on lab values classified per CTCAE criteria V 5.0 at Baseline (i.e., Study Week 0), the maximum grade observed, and the grade observed for the last value post Baseline will be tabulated. New Grade 3 CTCAE on treatment in selected laboratory results will be listed.

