### **10.3.9.7 Liver Function Tests Over Time**

Changes from Baseline in ALT and AST will be calculated for each subject and study visit. Missing values will be treated as missing.

Summary statistics (i.e., mean, median, standard deviation, maximum, and minimum, 25th and 75th percentiles) for the actual values, changes from Baseline, and maximum value observed post treatment will be tabulated for liver function tests by treatment group and study week. In addition, shifts based on the CTC grades in ALT, AST, and total bilirubin from the Baseline (i.e., Study Week 0) to the maximum observed value, and the last value post Baseline will be tabulated.

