AST/ALT is 5 x ULN or higher and total BL is less than 2 x ULN	
 
Interrupt study drug.
 
Recheck LFTs every 72 hours:
 
If AST and ALT decrease, recheck until ALT and AST are no longer elevated (below 1.5 x ULN) and total BL remains less than 2 x ULN; resume study drug at next lower daily dose (refer to Table 5).
 
If AST/ALT persist at 5 x ULN or higher for 2 weeks or more, discontinue study drug.
 

AST/ALT is 3 x ULN or higher and less than 5 x ULN	If patient is symptomatic (e.g., nausea, vomiting, abdominal pain): 
 
Interrupt study drug.
 
Recheck LFTs every 72 hours until ALT/AST values are no longer elevated (below 1.5 x ULN) and total BL remains less than 2 x ULN.
 
Resume study drug at next lower daily dose (refer to Table 5).
 

	If patient is asymptomatic: 
 
Recheck LFTs every 72 hours until ALT/AST are below 1.5 x ULN and total BL remains less than 2 x ULN.
 
Consider interruption or dose reduction of study drug if ALT/AST and TBL remain in this category (AST/ALT is 3 to 5 x ULN; and total BL remains less than 2 x ULN).
 

Adverse Reaction	Recommended Action
	
 
If interrupted, resume study drug at next lower daily dose (refer to Table 5) when ALT/AST are no longer elevated (below 1.5 x ULN) and total BL remains less than 2 x ULN.
 
If AST/ALT persist at 5 x ULN or higher for 2 weeks or more, discontinue study drug.
 

AST/ALT is 3 x ULN or higher and total BL >2 x ULN	
 
Check direct and indirect BL levels. If direct BL is >2x ULN then discontinue study drug, if only indirect BL is >2x ULN then monitor as above.
 

Elevated unconjugated (indirect) BL in absence of other LFT abnormalities	
 
Continue study drug since isolated increases in unconjugated (indirect) BL may be due to UGT1A1 inhibition or the underlying wAIHA disease.
 

Diarrhea	

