Diarrhea	
 
Manage diarrhea using supportive measures (e.g., dietary changes, hydration and/or antidiarrheal medication) early after the onset until symptom(s) have resolved.
 
If symptom(s) become severe (Grade 3 or above), temporarily interrupt study drug.
 
If diarrhea improves to mild (Grade 1), resume study drug at the next lower daily dose (refer to Table 5).
 

Neutropenia	
Neutropenia	
 
If absolute neutrophil count decreases (ANC less than <math>1.0 \times 10^9/L</math>) and remains low after 72 hours, temporarily interrupt study drug until resolved (ANC greater than <math>1.5 \times 10^9/L</math>).
 
Resume study drug at the next lower daily dose (refer to Table 5).
 

ALT = alanine aminotransferase; AST = aspartate aminotransferase; BP = blood pressure; BL = bilirubin; ULN = upper limit of normal; LFT = liver function tests (AST, ALT, total Bi with fractionation if elevated, alkaline phosphatase); AST/ALT = AST or ALT

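### The nominal-visit rule, read literally, leaves the 72-hour liver-test rechecks out of the worst-value and shift tables for ALT, AST and bilirubin

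*Combined protocol and SAP*

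**What the plan says.** - **General rule.** Section 10.3 opens by covering all efficacy and safety endpoints, then states: "Analysis will be based on nominal study visits (i.e., study Weeks 0 to 26". Sections 10.3.9.3 and 10.3.9.5 to 10.3.9.7 make no exception.
- **Laboratory tables.** For CTCAE shifts, section 10.3.9.3 says that "the maximum grade observed, and the grade observed for the last value post Baseline will be tabulated". Section 10.3.9.7 shifts ALT, AST and total bilirubin from Baseline "to the maximum observed value, and the last value post Baseline will be tabulated". Both sections also place the post-treatment maximum in tables by treatment group and study week.
- **Scheduled liver tests.** Table 4 has them after Baseline at Weeks 4, 8, 12, 16, 20, 22 and 24, and at Week 26 for subjects who do not enter the extension.
- **Rechecks.** From 3 x ULN, the hepatotoxicity rows of Appendix 2 say "Recheck LFTs every 72 hours", with or without symptoms. For ANC below 1.0 x 10^9/L the neutropenia row reads "remains low after 72 hours, temporarily interrupt study drug until resolved", which implies a repeat count.
- **Data capture.** Section 7.4: "Subject visits conducted outside of the scheduled protocol visits should be captured in the subject's medical record and CRF".
- **SAP.** Section 10.0 defers full detail to a SAP to be finalized before database lock. The combined document supplied contains no SAP text on unscheduled results.

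**The concern.** Hepatotoxicity is one of the recognized harms of this drug, and the shift to the worst grade is the table that a safety reader consults first. A value that peaks after first detection will often sit at a recheck, between scheduled visits. If the nominal-visit rule governs that table, the peak is in the database but not in the table.

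The loss would not be balanced between arms. Only subjects who trigger a recheck can lose a value. In the ITP trials, section 3.6.2.2 gives ALT/AST above 3 x ULN in 9% of fostamatinib patients and in no placebo patients. Any understatement would therefore fall mainly on the active arm and narrow the contrast with placebo.

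**Working it through.** The plan gives no figure to reproduce. The check compares the passages and then gauges the scale.

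**1. How many results fall off schedule.** At 72-hour spacing, rechecks strictly between visits 28 days apart fall on days 3, 6, ..., 27, which is up to 9. Between visits 14 days apart they fall on days 3, 6, 9 and 12, which is up to 4. One subject under recheck can thus have more unscheduled liver tests than the 7 scheduled from Week 4 to Week 24.

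**2. Does any safety section bring them back in?** No. The terms used for the maximum are general and do not mention unscheduled results. By contrast, section 10.3.6 defines eligible hemoglobin visits as scheduled ones and accepts central or local laboratories. The safety sections say neither. Section 10.3.9.6 averages repeat blood pressures within a visit, but no section says which laboratory value represents a visit when several fall in the same ±3-day window.

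**3. How many subjects are exposed.** Inputs: 45 fostamatinib subjects (section 10.1) and the 9% ITP rate (section 3.6.2.2). That the ITP rate carries over to wAIHA is an assumption. It is also a rate above 3 x ULN, while Appendix 2 acts at 3 x ULN or higher.

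- Expected number: 45 x 0.09 = 4.05.
- 95% binomial range: 1 to 8 subjects.
- Probability of at least one: 1 - 0.91^45 = 0.986.

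**4. How many would be graded too low.** This needs the height and timing of ALT peaks, which the documents do not give. As an illustration, excursions were simulated with these assumptions:

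- log-linear rise over 14 to 28 days and fall over 14 to 42 days (the fall resembles the 2 to 6 weeks of recovery in section 3.6.2.2);
- peaks lognormal with median 4 x ULN and log-SD 0.5;
- rechecks every 3 days for 42 days after the first scheduled value of at least 3 x ULN;
- no effect of drug interruption.

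| Rise/fall (days) | At least 5 x ULN, nominal visits | At least 5 x ULN, with rechecks | Gap (points) |
|---|---|---|---|
| 14/14 | 25.2% | 39.1% | 13.9 |
| 14/28 | 25.3% | 35.3% | 10.0 |
| 21/42 | 26.1% | 37.2% | 11.1 |
| 28/28 | 25.6% | 41.9% | 16.3 |
| 28/42 | 26.7% | 40.2% | 13.5 |

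Percentages are of detected cases. With 4.05 expected cases, the gap is 4.05 x 0.100 = 0.4 to 4.05 x 0.163 = 0.7 of one subject. At the upper end of the range it is 8 x 0.163 = 1.3 subjects. If every excursion stops rising at detection, for instance because drug is interrupted, the gap is zero.

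**The case against.** **The exclusion is inferred.** The rule in section 10.3 can be read as assigning data to planned weeks for by-visit tables, and a maximum observed value can be read as covering every result. Where the protocol restricts to scheduled visits it says so, as for hemoglobin. This stands in part: the text is ambiguous and does not state an exclusion. But two programmers could produce different tables from it, and the maxima tabulated by study week favor the literal reading.

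**The SAP may settle it.** It may. Nothing in the supplied document does.

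**Safeguards exist.** This stands. A reader might infer that off-schedule peaks would vanish from the report, and the documents do not support that. A laboratory result that changes dosing is recorded as an adverse event (section 7.13.4). Liver test elevation is a TEAE of interest (10.3.9.1). TEAEs leading to reduction, interruption or discontinuation are listed (10.3.9.2), and so are new Grade 3 laboratory results (10.3.9.3). Subjects meeting the first two Hy's Law criteria are notified to the Medical Monitor (9.5). None of these corrects a shift table, and the Grade 3 listing does not say that unscheduled results are included.

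**The simulation is fragile.** This also stands. Its table puts 28% to 39% of the cases at or above 5 x ULN in a lower category, and a reader might take that as an estimate. Varying the assumed peak (median 3 to 8 x ULN, log-SD 0.3 to 0.5) and rise (7 to 28 days) moves that share from under one fifth to over one half. It shows only that the effect on counts is small.

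**Conclusion.** The point holds for ALT, AST and total bilirubin as a wording gap: applied literally, the nominal-visit rule keeps collected recheck values out of the worst-value and shift tables. About 4 of 45 fostamatinib subjects would have such values if the ITP rate applies. The number misgraded cannot be computed from the documents and is probably one or fewer. The tables are descriptive, and no hypothesis test is affected. It is a small, cheap improvement to safety reporting.

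Two wider readings are tempting and are not supported:

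- **Blood pressure.** A reader might infer that its maxima are lost in the same way. Appendix 2 has no 72-hour blood pressure recheck; its rules concern persistence over 4 or 8 weeks, and repeat readings are taken within a visit. Blood pressure is affected only if a reading happens to be taken at an unscheduled visit.
- **Neutrophils.** ANC rechecks do not feed the liver tables. The clearer fault is in section 10.3.9.5, whose shift uses the maximum although neutropenia is a low count. Adding unscheduled results would not cure that.

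**What to change.** 1. In section 10.3, limit the nominal-visit rule to by-visit summaries, and say which laboratory value represents a visit when several fall in one window.
2. In sections 10.3.9.3 and 10.3.9.5 to 10.3.9.7, state that every worst post-Baseline value, worst CTCAE grade and worst-category shift uses all post-Baseline results, scheduled and unscheduled, central or local, including the Appendix 2 rechecks. Say the same for the Grade 3 listing.
3. In section 10.3.9.5, replace the maximum in the shift with the lowest count or worst grade.
4. In section 10.3.9.6, state whether the maximum uses visit means or single readings.

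If the final SAP already says this, a cross-reference from section 10.3 is enough.

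The cost is wording and programming. No new data are needed, clinical management is untouched, and by-visit summaries from scheduled samples do not change. One drawback: subjects under recheck contribute more measurements, which can raise their worst value somewhat, and more so in the arm with more rechecks. The size of that effect has not been computed; a table footnote should mention it.

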#### **10.3.1 Subject Disposition**

An accounting of study subject disposition, including total number of subjects screened, enrolled, randomized, early discontinuation of study, and study completers, will be presented by treatment group. In addition, a flow diagram detailing the disposition of subjects will be created. Also, a listing with the reasons for screen failures and study discontinuation will be provided.

#### **10.3.2 Enrollment Exceptions and Protocol Deviations**

Major protocol deviations related to study inclusion or exclusion criteria, conduct of the trial, subject management or subject assessment will be listed by site. Major protocol deviations are deviations that may significantly affect the completeness, accuracy, and/or the reliability of the study data or that might significantly affect a subject's rights, safety and well-being. Examples of major protocol deviations are:

- Subject enrolled who does not meet eligibility criteria
- Subject who used non-permitted rescue medications
- Improper collection of or failure to collect the initial study informed consent
- Subject who received treatment that was contrary to their randomization assignment
- Subject who developed withdrawal criteria during the study but was not withdrawn.

Protocol deviations will be maintained in the trial master file and will be listed and discussed in the clinical study report.

### **10.3.3 Demographic and Baseline Characteristics**

Baseline and demographic characteristics such as age, weight (kg), height (cm), body mass index (kg/m^2), ethnicity, race, sex, disease type (i.e., primary or secondary), duration of AIHA, Baseline corticosteroid use (Yes/No), number of unique prior AIHA therapies, prior AIHA therapies, splenectomy (Yes/No), rituximab (Yes/No), hemoglobin (g/dL), LDH (U/L), reticulocyte (10^9/L), and haptoglobin (g/L), at Baseline will be summarized by treatment group for the ITT population.

For continuous variables, number of observations, mean, median, standard deviation, minimum and maximum values, and 25th and 75th percentiles will be presented. For categorical variables, counts, and percentages will be tabulated for each category.

All randomly assigned subjects will be included in the analysis. Missing values will not be imputed.

### **10.3.4 Treatment Compliance**

Subject compliance with the assigned treatment will not be collected in the EDC system. The assessment of compliance will be based on site monitoring and pharmacy drug dispensation logs. All pharmacy logs will be kept in the trial master file.

### **10.3.5 Concomitant Therapy**

All medication used after the first protocol treatment to the end of study (Week 24/26) will be documented. Concomitant medications will be coded using the World Health Organization (WHO) Drug Dictionary. Prior medications that are ongoing at the time of study enrollment will also be recorded. All concomitant medications will be listed and summarized by treatment group.

### **10.3.6 Analysis of Primary Efficacy Endpoint**

The primary efficacy endpoint is achievement of durable hemoglobin response (Yes/No) defined as achieving a hemoglobin level  $\geq 10$  g/dL with an increase from Baseline in hemoglobin level of  $\geq 2$  g/dL on 3 consecutive available visits during the 24-week treatment period, in which hemoglobin measurements eligible for this definition occurred outside a Rescue Treatment Visit Exclusion Period.

Available visits are defined as any scheduled visit where a plasma sample was collected, and hemoglobin level analyzed using either central or local laboratory.

For permitted rescue medications, a Rescue Treatment Visit Exclusion Period begins with the initiation of the rescue medication. The end of a Rescue Treatment Visit Exclusion Period is 4 weeks (28 days) following the return of steroid use to Baseline level or the last administration of rescue medication, whichever event occurs the latest. Any hemoglobin measurements made during this exclusion period are not eligible for any endpoint definition.

For non-permitted rescue medications, a Rescue Treatment Visit Exclusion Period begins with the initiation of the rescue medication and ends at Week 24/Week 26 or date of early termination from study.

If durable hemoglobin response cannot be determined because the subject discontinued from the study prior to attaining a durable response, then the subject will be assumed as not having achieved a durable response.

Analysis will be performed after all randomized subjects have completed the 24 weeks of treatment or discontinued from the study. All subjects randomized will be included in the analysis (ITT population). The following hypothesis will be evaluated:

$$H_0: \Theta_{\text{Fostamatinib,Placebo}} = 1$$

$$H_a: \Theta_{\text{Fostamatinib,Placebo}} \neq 1,$$

where  $\Theta_{\text{Fostamatinib,Placebo}}$  is the odds ratio of durable hemoglobin response due to treatment.

Analysis will be performed using Cochran-Mantel-Haenszel (CMH) test stratified by concomitant steroid use at Baseline ( $\geq 20$  vs.  $< 20$  mg daily), and screening hemoglobin level ( $< 9$  vs.  $\geq 9$  g/dL). The odds ratio will be presented along with the 95% CI. The study will be considered to meet its primary efficacy objective if the lower bound of the 95% CI of the odds ratio of durable hemoglobin response between the Fostamatinib and Placebo-treated subjects is greater than 1.

In addition, the exact Clopper-Pearson 95% CI for the proportions and the Agresti-Min exact unconditional CI for the difference in proportions will be estimated.

The difference in proportion of durable hemoglobin response between the two treatment groups will be estimated and the 95% Miettinen-Nurminen score CIs will be computed taking into account the stratification factors.

A variety of sensitivity analyses of the primary analysis will be performed. These sensitivity analyses will consider:

- adjusting for prognostic variables for which an imbalance existed between the treatment groups at Baseline
- durable hemoglobin response derived using the hemoglobin values imputed
- changing the 4-week washout period in a Rescue Treatment Visit Exclusion Period to a 6-week washout period

Details will be provided in the SAP.

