#### 4.3 Secondary Efficacy Endpoints

The secondary efficacy endpoints within the 24 weeks of treatment are:

1. Hemoglobin response on at least one visit (Yes/No)
2. Achievement of a change from Baseline in hemoglobin level of 2 g/dL or greater (Yes/No)
3. Change in hemoglobin value from Baseline to End of Treatment (Week 14 to Week 24)
4. Use of permitted rescue medications after Week 4 (Yes/No)
5. Change from Baseline to Week 24 in Functional Assessment of Chronic Illness Therapy - Fatigue scale (FACIT-F)

End of Treatment hemoglobin is defined as the mean of the hemoglobin values from the last 6 available visits between Week 14 and Week 24, inclusive, as long as those visits occurred outside a Rescue Treatment Visit Exclusion Period.

The FACIT-F scale is a short, 13-item, easy to administer tool that measures an individual's level of fatigue during their usual daily activities over the past week. Each item is rated using a 5-point Likert-type scale (0 = not at all; 1 = a little bit; 2 = somewhat; 3 = quite a bit; and 4 = very much). Negatively stated items are reversed by subtracting the response from "4". After reversing proper items, all subscale items are summed to a total, which is the subscale score. All items contribute to the sum score with equal weight. The scale range is 0 to 52, with 0 being the worst possible score and 52 being the best possible score indicating no fatigue (see FACIT

Administration and Scoring Guidelines, and Cella 2002). The overall score will be calculated and prorated for missing items as follows:

$$\text{Total Score} = [\text{Sum of item scores}] \times [\text{N of items in subscale}] \div [\text{N of items answered}]$$

The FACIT-F change scores will be computed as (Week 24 score - Baseline score).

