**Table 4: Schedule of Procedures**

Study Procedure	Screening	Baseline	Weeks (allowed visit windows ±3 days)												Follow- Up g
	Day -28 to Day -1	Day 1 Wk 0	Wk 2	Wk 4 f	Wk 6	Wk 8	Wk 10	Wk 12	Wk 14	Wk 16	Wk 18	Wk 20	Wk 22	Wk 24/ Early Term	Wk 26 ± 3 days
Informed Consent	X														
Inclusion/Exclusion	X														
Demographics a	X														
Medical History	X	X													
Physical Exam	X													X	
Abbreviated Physical Exam		X	X	X	X	X	X	X	X	X	X	X	X		X
Adverse Events b	X	X	X	X	X	X	X	X	X	X	X	X	X	X	X
Height	X														
Weight	X							X						X	
KPS	X													X	
FACIT and EQ-5D c		X						X						X	
Concomitant Meds	X	X	X	X	X	X	X	X	X	X	X	X	X	X	X
Vital Signs d	X	X	X	X	X	X	X	X	X	X	X	X	X	X	X
12-Lead ECG	X														
Reticulocyte Count		X				X				X				X	X
Haptoglobin	X	X				X				X				X	X
DAT specific for anti-IgG or IgA e	X														
Complete Blood Count with Differential	X	X	X	X	X	X	X	X	X	X	X	X	X	X	X
Serum Chemistry with LFTs	X	X				X				X				X	X
LFTs				X				X				X	X		
Plasma for PK Samples			X	X				X			X				
Urinalysis	X	X				X				X				X	X
Serum Pregnancy Test h	X	X		X		X		X		X		X		X	X
Study Drug Dispensed		X		X		X		X		X		X			
Study Drug Accountability				X		X		X		X		X		X	

a. Demographics include sex, race/ethnicity and age.  
b. Adverse Events – Reporting period begins when the consent is signed.  
c. FACIT and EQ-5D – subject is to read questionnaire by him/herself and write/mark answers directly onto the questionnaire. When possible, administer the questionnaires at the start of the visit. Site staff to check only for completeness of each questionnaire.  
d. Vital Signs include blood pressure, pulse and temperature. All blood pressure determinations should be made with the subject seated and taken after the subject rests for 5 minutes. If the initial blood pressure at any visit, is ≥130 mmHg systolic or ≥ 80 mmHg diastolic (≥135 or ≥85 at screening), the subject should remain seated and blood pressure should be taken 2 additional times at least 3 minutes apart. If the average of the 3 BP measurements is ≥130 mmHg systolic or ≥80 mmHg diastolic, follow the dose modification recommendations in [Appendix 2](#).  

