### **7.13.4 Laboratory Tests**

Laboratory samples will be collected, processed, shipped and managed according to the lab manual. Samples will be obtained at each study visit according to the schedule in [Table 4](#). The total amount of blood collected for the duration of the 24-week study and 28-day screening period study is approximately 200 mL.

The following tests are to be collected and analyzed for the study:

- DAT specific for anti-IgG. Eligibility may be based on a historical DAT obtained within 12 months of the screening visit from a local laboratory, provided that specific IgG positivity is documented; otherwise, this assay will be done at screening by a central laboratory;

- Haptoglobin;
- Hematology: hemoglobin; red blood cell count (RBC); white blood cell count (WBC), platelet count, hematocrit, WBC differential count (neutrophils, lymphocytes, eosinophils, monocytes, and basophils), mean corpuscular hemoglobin concentration (MCHC), mean corpuscular hemoglobin (MCH), mean corpuscular volume (MCV), mean platelet volume (MPV), and red blood cell distribution width (RDW);
- Serum Chemistry: includes Na, K, Cl, bicarbonate (CO2), Ca, PO4, blood urea nitrogen (BUN), creatinine, globulin, random glucose, LDH, AST, ALT, alkaline phosphatase, total bilirubin, direct and indirect bilirubin, total protein, albumin;
- Reticulocyte count;
- Liver Function Tests: includes ALT, AST, alkaline phosphatase, LDH, total, direct and indirect bilirubin; and
- Urinalysis (UA): appearance, glucose, ketones, blood, protein, nitrate, bilirubin, specific gravity, pH, urobilinogen, and leukocytes. A microscopic urinalysis will be performed if protein, leukocyte esterase, blood, or nitrite are abnormal.

An abnormal laboratory value is clinically significant if it meets any of the following criteria, and as such should be documented on the AE page of the eCRF:

- Test result is associated with accompanying symptom;
- Test result requires additional diagnostic testing or medical/surgical intervention;
- Test result leads to change in study drug dosing or discontinuation from the study, significant additional concomitant drug treatment, or other therapy; or
- Test result is considered an AE by the Investigator or Sponsor.

Any laboratory result abnormality fulfilling the criteria for an SAE should be reported as such, in addition to being recorded as an AE.

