### 7.13.6 Pharmacokinetic Samples

Plasma will be collected according to the schedule in [Table 4](#) for PK analysis. PK will be drawn at the Week 2, 4, 12, and 18 visits. The timing of the PK sampling as well as the date and time of the last dose of study drug will be recorded. Subjects are not required to take study drug in the clinic the day the sample is collected. Samples will be shipped to and stored at the central laboratory at -70°C during the course of the study. Samples will then be transferred to and analyzed at the corresponding bioanalytical laboratory.

After completion of the study, samples may be stored for an additional 5 years for further metabolite identification and/or evaluation of the bio-analytical method in relation to this study. Data from these analyses will be used by Rigel for internal research purposes related to this study and will not be included in the clinical report. All samples will be destroyed after analysis or expiration of the 5-year time period.

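### Section 10.3.6 ties an available visit to a plasma sample; read literally, that leaves 4 of the 12 on-treatment hemoglobin visits, very probably through a slip for blood sample that should be corrected before database lock

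*Combined protocol and SAP*

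**What the plan says.** Section 10.3.6 defines the unit on which the primary endpoint is counted: "Available visits are defined as any scheduled visit where a plasma sample was collected, and hemoglobin level analyzed using either central or local laboratory". Durable response needs hemoglobin of at least 10 g/dL and a rise of at least 2 g/dL from Baseline "on 3 consecutive available visits during the 24-week treatment period".

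Two other endpoints use the same term. In section 4.3, End of Treatment hemoglobin is "the mean of the hemoglobin values from the last 6 available visits between Week 14 and Week 24". Section 4.5 lists the percentage of available visits with hemoglobin response.

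On sampling:

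- **Plasma.** Table 4 has one visible plasma row, "Plasma for PK Samples". Section 7.13.6 gives its purpose and timing: "PK will be drawn at the Week 2, 4, 12, and 18 visits".
- **Hemoglobin.** Section 7.13.4 lists it in the hematology panel ("Hematology: hemoglobin; red blood cell count (RBC"). The Table 4 row "Complete Blood Count with Differential" is marked at every visit, including all twelve from Week 2 to Week 24. Sections 5.8 and 7.3 also say that hemoglobin is measured at each visit.

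**The concern.** The definition sets two conditions joined by *and*: a plasma sample was collected, and hemoglobin was analyzed. No visible text links a hemoglobin result to a plasma sample. The sample named in the rule is therefore not the one that yields hemoglobin, and in the visible schedule it is drawn at only a third of the relevant visits.

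The term governs the primary endpoint, the third secondary endpoint in the hierarchical order of section 10.4, and one additional efficacy endpoint. A literal derivation would go wrong in two directions:

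- It would miss durable responses that begin after Week 4, which is when the dose increase in section 7.8.1 starts. Section 5.1 reports first responses in Phase 2 from Week 2 to as late as Week 30.
- It would treat Weeks 4, 12 and 18 as consecutive whatever the hemoglobin was at Weeks 6, 8, 10, 14 and 16, so a response lost in between could still count as durable.

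If the wording were corrected only after unblinding, the correction could look like a post hoc redefinition of the primary endpoint.

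**Working it through.** **1. Count the visits.** From Table 4 and section 7.13.6, on treatment and after Baseline:

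| Reading | Available visits (weeks) | Number |
|---|---|---|
| CBC schedule | 2, 4, 6, 8, 10, 12, 14, 16, 18, 20, 22, 24 | 12 |
| Literal plasma rule | 2, 4, 12, 18 | 4 |
| Excluded by the literal rule | 6, 8, 10, 14, 16, 20, 22, 24 | 12 − 4 = 8 |

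**2. Count the runs of three consecutive available visits.** With *v* visits, all sampled, there are *v* − 2 runs.

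- CBC schedule: 12 − 2 = 10 runs. The earliest is complete at Week 6 and the latest starts at Week 20.
- Literal rule: 4 − 2 = 2 runs, namely 2-4-12 and 4-12-18. The earliest is complete at Week 12.

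The count of two assumes complete sampling. A missed Week 4 sample would make 2-12-18 a run, and a missed Week 12 sample would make 2-4-18 one. The consequence for late responses does not need that assumption: after Week 4 only Weeks 12 and 18 remain, and two visits cannot supply three.

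**3. End of Treatment window, Weeks 14 to 24 inclusive.** The CBC schedule gives Weeks 14, 16, 18, 20, 22 and 24, six visits and exactly the number in section 4.3. The literal rule gives Week 18 alone.

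**4. Percentage of available visits with response.** The largest possible denominator is 12 on the CBC schedule and 4 under the literal rule.

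**5. Power, as an illustration only.** Inputs from section 10.1: 27% (7/26) against 5%, 45 per group, two-sided 0.05, Fisher's exact test, stated power at least 84%. Power is the sum, over all pairs of responder counts for which the two-sided Fisher p-value is at most 0.05, of the product of the two Binomial(45, *p*) probabilities.

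The plan's own figure first. At 27% against 5% this gives 78.0% (77.7% at exactly 7/26), so the stated 84% does not reproduce with the named test. Fisher with 4% on placebo gives 84.1%; normal approximations at 27% against 5% give 82.4% (pooled) and 84.7% (unpooled). That is a separate matter and neither supports nor weakens this point. The comparator used below is 78.0%.

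Now let a share *f* of durable responders be retained under the literal rule, the same in both arms. The rates become 27% × *f* and 5% × *f*:

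| *f* (assumed) | Fostamatinib | Placebo | Fisher power |
|---|---|---|---|
| 100% | 27.0% | 5.0% | 78.0% |
| 75% | 20.25% | 3.75% | 59.6% |
| 50% | 13.5% | 2.5% | 31.3% |
| 25% | 6.75% | 1.25% | 4.9% |
| 20% | 5.4% | 1.0% | 2.2% |

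The last row corresponds to onset spread evenly over the ten visits from Week 2 to Week 20, with response sustained to Week 24: two of the ten onsets (Weeks 2 and 4) are early enough, and 2/10 = 20%. The documents give no onset distribution, so no row is preferred.

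**The case against.** The strongest reply is that the protocol resolves the point itself. Section 4.3 expects six available visits between Week 14 and Week 24, which only the CBC schedule can supply. Sections 5.8 and 7.3 require hemoglobin at each visit. The Phase 2 durable response in section 10.1 is counted on scheduled visits, with no plasma condition. Section 10.3.6 also speaks of a central or local laboratory, whereas section 7.13.6 sends PK plasma to the central laboratory for storage and then to a bioanalytical laboratory. The natural reading is a single sample, tested for hemoglobin and misnamed. All of this stands, and it makes the point a correction of wording rather than a dispute about design.

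Two limits also stand:

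- Section 7.13.7 is redacted, and a redacted item among the Baseline assessments in section 7.2 refers to it. A further plasma sample cannot be excluded, so *only at Weeks 2, 4, 12 and 18* rests on the visible schedule.
- Section 10.0 leaves the complete analysis plan to a SAP finalized before database lock. The text available for this review contains no separate SAP derivation, so it cannot be shown that the slip has reached the programming.

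A reader might infer that the trial is left with about 2% power. The documents do not support that. The figure is the lowest row of an assumed range, it assumes equal retention in both arms, it ignores lost responses that the literal rule would wrongly count, and it uses the sizing test rather than the stratified Cochran-Mantel-Haenszel analysis. Above all, it describes a reading that nobody is likely to program.

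What the reply does not remove is that the operative sentence for the primary endpoint states a condition that contradicts section 4.3 on the visible schedule. The derivation should not depend on an unstated interpretation.

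**Conclusion.** The definition is wrong as written and should be corrected. On the visible schedule its literal effect is exact: 4 of 12 on-treatment visits available, no durable response possible from an onset after Week 4, and one End of Treatment visit instead of six. With complete sampling, 2 qualifying runs remain instead of 10. These counts rest on Table 4 and section 7.13.6, and on there being no other plasma sample in redacted section 7.13.7.

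It is very probably a slip for blood. The counts show what the sentence says, not what the trial intends or will do. The power range of 78% down to 2% depends wholly on the assumed share of responders retained and is not a predicted consequence.

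**What to change.** Before database lock, replace the plasma condition in section 10.3.6 with *a blood sample for CBC was collected*, so that any scheduled visit from Week 2 to Week 24 with a hemoglobin result, central or local, is available. Use the same definition in the SAP for the primary endpoint, End of Treatment hemoglobin and the percentage of available visits with response.

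The cost is one phrase in the protocol and matching text in the SAP. No visit, blood draw or sample size changes, and the corrected definition gives the six End of Treatment visits that section 4.3 already expects.
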